#### 4.6.2 Evaluable Patients

##### 4.6.2.1 Immune Response Evaluable

For a patient to be evaluable for immunomodulation by assigned drugs, the patient must be on treatment for 6 weeks (when first assessment of peripheral immunoscore will be conducted). Any patient who is taken off study prior to completion of 2 cycles (=6 weeks) must be replaced.

## **4.7 Multi-Institutional Trial Coordination**

### **4.7.1 Personnel**

At each site, personnel dedicated to this protocol will be:

- A study PI
- A research coordinator
- A data manager

In addition, the Georgetown Multicenter Project management office will play the primary role in coordinating the trial between Lombardi-Georgetown and additional sites. This Multicenter Project Managers will be the main point of contact for [name] and the other site PIs for any study related concerns, and to confirm eligibility of each patient being considered for enrollment (Including “remote” confirmation of eligibility for the patients being screened at other sites). The Project Manager(s) will also be the point of contact for the data managers for data entry questions. Finally, the Project managers will play a major role in regulatory coordination of the study, specifically by: 1) Reviewing and confirming all study-related adverse events; 2) Ensuring that sites are submitting all severe adverse event (SAE) reports to the site IRB per local IRB policy ; 3) Gathering and preparing all necessary primary source data for review/audit.

### **4.7.2 Patient Enrollment**

If a patient is being screened for enrollment, the local research coordinator must send an email within 24 hours containing the patient’s initials to the local PI, to [name], and to the Project Managers. If a patient is successfully screened, the local research coordinator must send all supporting documentation to the Project Managers(by secure email). Patients should not start therapy until [name] and the Project Managers have reviewed the patient’s records and confirmed that the patient is indeed eligible for enrollment.

### **4.7.3 Data Collection and Management**

Patient data will be entered into the on-line accessible database. This database is housed at Lombardi-Georgetown, but is accessible anywhere there is internet access. The data manager and research coordinator at each site will attend an on-line training session so that they may learn how to enroll data into the database. All screening data should be entered prior to starting therapy, and all ongoing patient data should be entered within 10 business days of each patient visit.

### **4.7.4 Conference Calls**

A biweekly conference call will be held between Lombardi-Georgetown and the other sites to review patient enrollment, toxicity, and response assessment.

#### 4.7.5 Trial Auditing

The multicenter Project Manager will request primary source documents for the patients to be audited. This will include collecting copies of the primary source data for any patients treated at other sites.

### **5.0 TREATMENT PLAN**

If a subject randomizes to Arm A, nivolumab will be provided by the study.

If a subject randomizes to Arm B, medication is not covered by the study and will be handled similarly to standard of care medication administration. Therapy will be based on the patient's actual weight. Dose adjustments will be made according to the approved label and at the discretion of the treating physician.

If a subject randomizes to Arm C, nivolumab will be provided by the study and capecitabine will be covered by patient's insurance.

Administration of nivolumab and/or capecitabine must be initiated within 2 weeks from enrollment in the study arm.

#### **5.1 Dose modifications - General Guidelines**

Participants will be monitored continuously for AEs while on study therapy. Participants will be instructed to notify their physician for any and all AEs. Modifications should be applied by the investigator's judgment. In case of an AE relationship assignment to capecitabine alone, dose modifications for capecitabine alone are allowed. In case of doubt, both chemotherapy and nivolumab doses should be modified. Also, in case of assignment of AE relationship to nivolumab alone, dose reduction for chemotherapy is not mandated. Specific algorithms for the management of immune-related AEs are provided in Appendix D and are applicable to immune-related AEs for all immuno-oncology study treatment combinations. For capecitabine chemotherapy, the package insert and local standard of care rules for dose reduction should also be applied.

#### **5.2. Nivolumab**

Nivolumab will be given at flat dose of 360 mg iv every 3 weeks for 6 cycles.

##### **5.2.1. Dose Modifications**

Immuno-oncology (I-O) agents are associated with AEs that can differ in severity and duration

from AEs caused by other therapeutic classes. Early recognition and management of AEs associated with I-O agents may mitigate severe toxicity. Management algorithms have been developed from extensive experience with nivolumab to assist investigators in assessing and managing the following groups of AEs:

- Gastrointestinal
- Renal
- Pulmonary
- Hepatic
- Endocrinopathies
- Skin
- Neurological

Specific algorithms for the management of immune-related AEs are provided in Appendix D and are applicable to immune-related AEs for all immuno-oncology study treatment combinations (Arm A and C).

Nivolumab dose modifications do not apply.

For an AE requiring dose modification, chemotherapy, and/or nivolumab should be interrupted to allow recovery from the AE. Re-initiation of study treatment cannot occur until the AE decreases to  $\leq$  Grade 1 or baseline assessment. In case of delayed recovery to  $\leq$  Grade 1 or baseline from treatment-related AEs that result in a delay of treatment for  $> 42$  days, the participant will not receive additional protocol-related therapy and will be removed from study unless discussed and agreed upon by the Investigator and Sponsor/Medical Monitor that it is in the best interest of the participant to receive additional therapy with nivolumab.

Withhold nivolumab for any of the following:

- Grade 2 pneumonitis
- Grade 2 or 3 diarrhea or colitis
- Aspartate aminotransferase (AST) or alanine aminotransferase (ALT) greater than 3 and up to 5 times upper limit of normal (ULN) or total bilirubin greater than 1.5 and up to 3 times ULN
- Creatinine greater than 1.5 and up to 6 times ULN or greater than 1.5 times baseline
- Any other severe or Grade 3 treatment-related adverse reactions
- Grade 2 hypophysitis
- Grade 2 adrenal insufficiency
- New-onset moderate or severe neurologic signs or symptoms

Resume nivolumab in patients whose adverse reactions recover to Grade 0-1.

Permanently discontinue nivolumab for any of the following unless approved by the Sponsor/Medical Monitor:

- Any life-threatening or Grade 4 adverse reaction
- Grade 3 or 4 pneumonitis
- Grade 4 diarrhea or colitis
- AST or ALT greater than 5 times ULN or total bilirubin greater than 3 times ULN
- Creatinine greater than 6 times ULN
- Any severe or Grade 3 treatment-related adverse reaction that recurs
- Inability to reduce corticosteroid dose to 10 mg or less of prednisone or equivalent per day within 12 weeks
- Persistent Grade 2 or 3 treatment-related adverse reactions that do not recover to Grade 0-1 within 12 weeks after last dose of nivolumab
- Grade 3 or 4 adrenal insufficiency
- Immune-mediated encephalitis
- Grade 3 myocarditis

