Version 6	16JUL2019	
Protocol Updates:
 
 
Page 18, 20, Appendix E: Added Quality of Life Questionnaires
 
Fixed minor administrative discrepancies throughout the protocol
 
Page 34: Made clarifications regarding dose delays for correlative specimen collection
 
Page 35: Clarifications on temporary suspension of treatment and dose interruptions
 
Page 38: Updated the SAE reporting guidelines from BMS for subsites
 
Page 48: Updated specimen labeling section to be consistent with the lab manual
 
 
ICF Updates:
 
 
Page 3-4: Added information on biopsy(ies)
 

Version 6.1	09Mar2020	
Protocol Updates:
 
 
PI changed from [name] to [name] throughout protocol.
 
Section 6.7 removed typo “atezolizumab or placebo”
 
Other Administrative clarifications/corrections made throughout protocol to replace CRO with Multicenter Project Managers and SAE reporting
 
Updates made to incorporate information from Protocol Clarification letters:
 

		
 
• Inclusion Criteria 2 changed “must have” to “should be” and a Note Added for clarification “(Note: As long as tissue sample is confirmed shipped, the subject will be eligible)”
 
• Inclusion Criteria 5 typo correction made
 
• Inclusion Criteria 8 added clarification “(Patients that meet the definition of asymptomatic subclinical hypothyroidism will be eligible to participate)”
 
• Section 6.3 added clarification “Note: Assessments performed for clinical indications (not exclusively to determine study eligibility) may be used for screening/baseline values even if the studies were done before informed consent was obtained.
 

Version 6.2	06 OCT 2020	
 
• Section 1.6.2 Administration of PRO questionnaires corrected to be consistent with table of events
 
• Section 5.2.1: corrected delay of treatment to >42 days to fix discrepancy between this section and Section 6.7. added the term “diarrhea” to be consistent with Appendix D clarified Permanently discontinue nivolumab “unless approved by the Sponsor/Medical Monitor”
 
• Appendix D: GI Adverse Events: updated to be consistent with section 5.2.1 and fixed typographical errors.
 

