### 2.2 Secondary objectives:

- 1). To determine the incidence of toxicity graded using the National Cancer Institute CTCAE v. 4.0 until 30 days after last dose of treatment on trial.
- 2). To determine association between changes in PIS from baseline to week 6 and week 12 and clinical outcome variables (DRFS and OS at 2-years)). After end of study visit, clinical follow up or telephone communication every 3months.
- 3). To describe the following endpoints and compare them between arms: DRFS, OS
- 4) Translational endpoints:
  - a) Circulating-tumor DNA (ct-DNA)

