## **4.4 Additional Study Restrictions**

### **4.4.1 Other Anticancer Therapy**

For purposes of this protocol, anti-tumor treatment may be defined as, but is not limited to, anti-cancer agents (endocrine therapy, cytotoxic chemotherapy, immunotherapy, or biologic therapy), radiotherapy, and investigational agents. An investigational agent is any drug or therapy not currently approved for use in humans. No other anticancer therapy is permitted during the course of the study treatment for any patient (the patient can receive a stable dose of corticosteroids during the study as long as these were started at least 4 weeks prior to enrollment and the total daily dose does not exceed 10mg of prednisone, or the equivalent, per exclusion criteria above). If the patient discontinues study treatment, this restriction no longer applies, however the patient will remain enrolled in the study for the purpose of collecting subsequent outcomes. Radiotherapy is not allowed.

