## 6.0 STUDY PROCEDURES AND TREATMENT ASSIGNMENT

### 6.1. Table of events

	Pre-registration	Screening	On Study (maximum 6 cycles; cycle is every 21 d)	Treatment discontinuation	Surveillance
	Post-surgery	-30 days	D1 of each cycle +/- 7 days. Each cycle is 21 days.	30 days (+/-7 days) after last dose	
Assessments					
Informed consent	X				
Medical history and height		X			
Physical examination		X	X ^	X	
Weight, BP		X	X ^	X	
ECOG PS		X	X ^	X	
CMP		X	X	X	
Creatinine clearance		X	X	X	
CBC with differential		X	X	X	
Breast imaging (remaining tissue only)					Yearly +/- 30 days
Adverse event and con meds assessment		X	X ^		
Urine pregnancy or serum HCG for WOCBP only		X	X ^ (every 3 weeks) for Arm A and C		
ACTH and Thyroid Function Tests#		X	X ^ (week 12) for Arm A and C	X	
Hepatitis and HIV screening*		X			
EORTC QLQ-C30 &		X	X (week 6)	X	
Telephone communication or focused physical exam+					Every 3-6 months
Treatment					
			Nivolumab 360mg iv q3w; capecitabine 1250mg/m  D1-14		

Correlative Samples					
Tumor from initial diagnosis		X (if available)			
Tumor from definitive surgery – with IHC testing for MSI	X				
Serum for peripheral immunoscore			X ^ (baseline, week 6 and 12)	X (if recurrence)	
Blood for ct-DNA \$			X ^ \$ (baseline, week 6 and 12)	X (if recurrence)	
Tumor from metastatic site				X (if recurrence)	

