#### **6.7. Treatment discontinuation**

A participant will be discontinued from the protocol therapy under the following circumstances:

- if there is evidence of progressive disease
- if the treating physician thinks a change of therapy would be in the best interest of the participant
- if the participant withdraws consent to protocol treatment
- if the drug exhibits unacceptable adverse events. Participants will be followed until the resolution of these adverse events.
- if a participant becomes pregnant

Patients may temporarily suspend study treatment if they experience an adverse event that requires a dose to be held. If study treatment is held because of adverse events for > 42 days beyond what was planned, then the patient will be discontinued from any study drug and be followed for safety. If, in the judgment of the investigator, the patient is likely to derive clinical benefit from resuming nivolumab and/or capecitabine after a hold > 42 days, study drug may be restarted with the approval of the Medical Monitor.

Dose interruptions for reason(s) other than adverse events, such as surgical procedures, may be allowed with Medical Monitor approval. The acceptable length of interruption will depend on agreement between the investigator and the Medical Monitor.

After treatment discontinuation, in the event of a continuing AE, patients must be followed up until resolution or stabilization of the AE.

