### **6.8. Surveillance**

Participants will be monitored by their treating physicians for the development of either local (chest wall, axillary, or supraclavicular nodes) or distant recurrent disease, and survival, at least once every 3 months for the first two years, then at least every 6 months during year 3. Surveillance will be done through telephone communication, focused physical exam or review of medical records. Surveillance for immune-related adverse events will be included in these follow up visits or telephone calls. The Principal Investigator will notify the Data Safety Monitoring Board of any serious adverse events and immune related adverse events that are believed to be related to prior drug treatment or study procedures that occur at any time after a patient has discontinued treatment.

For those patients that develop a recurrence while on active treatment or during the follow up period (i.e. 3 years), blood correlatives (ctDNA and PIS) and tissue biopsy will be obtained. Tissue for research will only be requested (one block or 13 unstained slides) if a biopsy is done as part of routine care, either to confirm metastatic disease and/or to repeat markers.

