### **8.5.2. Analysis for the Secondary Endpoint**

The observed incidence of toxicity will be tabulated according to the grade level and the attribution using the National Cancer Institute CTCAE v. 4.0. Fisher's Exact test will be used to compare the incidence rate of toxicity between treatment groups. We expect that among

patients with TNBC and residual disease at the time of surgery, those who receive post-surgery immunotherapy (ARM A and C) will have longer invasive disease-free survival (DRFS) time compared to those who receive post-surgery chemotherapy alone (ARM B). Patients will be followed for DRFS and overall survival (OS) for 3 years. The Kaplan-Meier method will be used to analyze the DRFS and OS. The DRFS and OS at year 2 will be presented with their 95% confidence intervals. Log-rank test will be used to compare the DRFS and OS between treatment groups.

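### Section 5.2.1 removes a patient from study after a toxicity hold of more than 42 days, while 6.7, 4.4.1, 6.8 and 8.5.2 keep that patient in follow-up (minor; secondary endpoints only)

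*Combined protocol and SAP*

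**What the plan says.** Section 5.2.1 (Dose Modifications, under Nivolumab) covers treatment-related adverse events whose slow recovery delays treatment by more than 42 days. Its consequence is that "the participant will not receive additional protocol-related therapy and will be removed from study", with an exception if the Investigator and the Sponsor/Medical Monitor agree that more nivolumab is in the participant's interest.

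Four other current sections bear on the same patient:

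- Section 6.7, for an adverse-event hold of more than 42 days beyond plan: "then the patient will be discontinued from any study drug and be followed for safety". Restart is possible with Medical Monitor approval.
- Section 4.4.1, for any patient who discontinues study treatment: "the patient will remain enrolled in the study for the purpose of collecting subsequent outcomes".
- Section 6.8 has participants monitored for local or "distant recurrent disease, and survival, at least once every 3 months for the first two years", then at least every 6 months in year 3.
- Section 8.5.2: "Patients will be followed for DRFS and overall survival (OS) for 3 years".

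None of these four excepts a patient stopped for a long hold.

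**The concern.** Section 6.7 covers adverse events in general and 5.2.1 only treatment-related ones, so every 5.2.1 case is also a 6.7 case. The trigger is 42 days in both, and both allow resumption by agreement. The conflict is therefore confined to patients who do not resume: one section takes them off study and the others continue to follow them.

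If a site acted on 5.2.1 literally, DRFS and OS would be censored at a time fixed by toxicity. Toxicity may be related to prognosis and may differ by arm, and the removal wording sits under the nivolumab heading. The censoring would then be potentially informative in the Kaplan-Meier estimates and log-rank comparisons of 8.5.2. Such a patient could also have week-6 and week-12 PIS values but no 2-year outcome for the association analysis in the secondary objectives.

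**Working it through.** The plan gives no figure on this point, so there is nothing to reproduce. The check has two parts: the wording, and the follow-up at stake per patient.

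**Wording.** The 5.2.1 sentence has two consequences joined by a conjunction: no more protocol therapy, and removal from study. Since the first already ends treatment, the second, read literally, adds something. Sections 6.7, 4.4.1, 6.8 and 8.5.2 contain only the first and continue follow-up. Section 6.7 by itself promises safety follow-up only; the outcome follow-up comes from the other three.

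**Timing of removal.** Inputs:

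- 21-day cycles, maximum 6 (6.1).
- A delay exceeds the limit on its 43rd day (5.2.1).
- g = days from study enrollment to cycle 1 day 1, taken as 0 to 14. Section 5.0 requires treatment to start within 2 weeks of enrollment in the study arm. DRFS runs from study enrollment (8.4.2), so this treats the two enrollment dates as the same.
- Holds begin at a planned cycle start, visits fall on planned dates, and there is no earlier delay.
- Only patients who completed 2 cycles are counted, because 4.6.2.1 and 8.5.1 require replacement of those taken off earlier. That leaves holds at cycle k = 3 to 6.

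Day of removal after enrollment = g + 21(k − 1) + 43.

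| Cycle held | Removal day (g = 0 to 14) | Days lost of 730 | Days lost of 1095 |
|---|---|---|---|
| 3 | 85 to 99 | 645 to 631 | 1010 to 996 |
| 4 | 106 to 120 | 624 to 610 | 989 to 975 |
| 5 | 127 to 141 | 603 to 589 | 968 to 954 |
| 6 | 148 to 162 | 582 to 568 | 947 to 933 |

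- Year 2: 568/730 = 78% to 645/730 = 88% of the period lost.
- Year 3: 933/1095 = 85% to 1010/1095 = 92% lost.

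**Effect on an arm's 2-year proportion.** With 15 per arm (8.2) and no other early censoring, one event-free patient of unknown 2-year status leaves at most 1/15 = 6.7 percentage points undetermined.

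**Primary endpoint.** The week-6 sample is due 42 days after cycle 1 day 1. The earliest removal in the table is 43 + 42 = 85 days after it. A patient who does not complete 2 cycles is non-evaluable and replaced whichever reading is used. The primary analysis does not change.

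**Safety.** SAE reporting for 100 days after dosing stops (7.1), non-serious AE collection for at least 30 days after the last dose (7.2.1.1), and follow-up of continuing events (6.7) all run from the end of treatment. A literal removal would mainly cost the scheduled surveillance contacts of 6.8.

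**The case against.** The strongest answer is that this protocol often uses the word study for the treatment phase. The Table of Events heads the treatment column "On Study (maximum 6 cycles; cycle is every 21 d"). Section 2.2 places outcome contact later: "After end of study visit, clinical follow up or telephone communication every 3months". Sections 4.6.2.1 and 8.5.1 speak of being off study in a rule about completing 2 cycles. The exception in 5.2.1 is itself about receiving more nivolumab. On this view the second half of the sentence is redundant drafting, and a site would have to let one phrase in a dosing subsection override four others before any follow-up was lost. Most of this stands, and the treatment-phase reading is quite possibly the intended one. It does not remove the point: the sentence ends therapy separately, and nothing in 5.2.1 tells a site which reading to use.

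A reader might go further than the documents allow in three ways.

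- **That the plan ends outcome follow-up for these patients.** No section says that removal stops outcome collection; that is an inference from one phrase, against 4.4.1 in particular.
- **That the sponsor meant the consequences in 5.2.1 and 6.7 to match.** The version 6.2 entry in the Document History says the delay in 5.2.1 was corrected "to fix discrepancy between this section and Section 6.7". It concerns the day count. It is silent on the consequence, and leaving the wording alone is equally consistent with regarding the two as equivalent.
- **That losses reach 91% of the time to year 2.** A hold at cycle 2 with g = 0 would give removal on day 21 + 43 = 64 and 666 of 730 days lost. That patient has not completed 2 cycles and must be replaced, so the arm would have more than 15 randomized patients and 1/15 would not apply.

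**Conclusion.** The inconsistency is real and in current text, but minor. Its consequence depends on a literal reading that the rest of the protocol makes less likely, and it touches only the secondary DRFS and OS analyses and the PIS-outcome association. The documents give no rate of holds beyond 42 days, so the number of patients affected is unknown and may be zero.

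For a patient who is affected, removal would fall 85 to 162 days after enrollment, with 78% to 88% of the time to year 2 and 85% to 92% of the time to year 3 lost. This rests on planned visit dates, no earlier delay, holds at cycle starts, and 0 to 14 days from study enrollment to first dose. The ±7-day visit windows, earlier delays, or study enrollment preceding arm assignment would shift these bounds.

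The 6.7 points per patient should not be read as bias. It is the width of what is unknown if nothing is assumed after removal. Kaplan-Meier uses the time observed, and the actual bias depends on how far removed patients differ from those who stay, which the documents do not let anyone estimate.

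**What to change.** In 5.2.1, replace the clause on removal from study with: *will be discontinued from study treatment and followed for safety, DRFS and OS per 6.7 and 6.8*. Keep the existing exception for agreement between the Investigator and the Sponsor/Medical Monitor.

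The cost is one phrase in the next amendment. It adds no visits and no data, because 6.8 already schedules the contacts and allows them by telephone, focused examination or record review. If the treatment-phase reading was always intended, the change alters nothing in practice and removes the doubt.

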## Skin Adverse Event - Management Algorithm

Rule out non-inflammatory causes. If non-inflammatory cause, treat accordingly and continue I-O therapy.

[figure not shown]
Patients on IV steroids may be switched to an equivalent dose of oral corticosteroids (e.g. prednisone) at start of tapering or earlier, once sustained clinical improvement is observed. Lower bioavailability of oral corticosteroids should be taken into account when switching to the equivalent dose of oral corticosteroids.

\*Refer to NCI CTCAE v4 for term-specific grading criteria.

^If SJS/TEN is suspected, withhold I-O therapy and refer patient for specialized care for assessment and treatment. If SJS or TEN is diagnosed, permanently discontinue I-O therapy.

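### Section 5.2.1 and the Appendix D skin note are not aligned on nivolumab after diagnosed SJS or TEN, and no text says which one governs

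*Combined protocol and SAP*

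**What the plan says.** The readable note under the skin algorithm in Appendix D has two steps. On suspicion: "If SJS/TEN is suspected, withhold I-O therapy and refer patient for specialized care for assessment and treatment". On diagnosis: "If SJS or TEN is diagnosed, permanently discontinue I-O therapy". The trigger is the diagnosis, not a grade, and that line states no exception.

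Section 5.2.1 works mainly by grade, through two lists that name neither SJS nor TEN.

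- The withhold list includes "Any other severe or Grade 3 treatment-related adverse reactions". It is followed by the instruction "Resume nivolumab in patients whose adverse reactions recover to Grade 0-1".
- The second list opens with "Permanently discontinue nivolumab for any of the following unless approved by the Sponsor/Medical Monitor". Its items include "Any life-threatening or Grade 4 adverse reaction" and "Any severe or Grade 3 treatment-related adverse reaction that recurs". It also names some diagnoses without a grade, such as "Immune-mediated encephalitis".

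The two places are linked. Section 5.2.1 lists skin among the adverse event groups that have algorithms and says the Appendix D algorithms apply to immune-related events in arms A and C. Section 5.1 also points to Appendix D. The opening of Appendix D, however, describes its contents as guidance that discussion with the Medical Monitor may supplement.

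**The concern.** For the same diagnosis, the two places can be read to different results. The appendix note ends treatment. The 5.2.1 lists, taken alone, either hold nivolumab and resume it, or stop it permanently subject to a waiver. Neither section says which text prevails.

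What is at stake is the safety of an individual patient in a nivolumab arm. Whether nivolumab is restarted after a diagnosed SJS or TEN could depend on which part of the protocol the site works from, or on whether the waiver is thought to reach the case.

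**Working it through.** No arithmetic bears on the mismatch itself, so the check sets the texts side by side. The documents do not grade SJS/TEN; the skin page refers to CTCAE v4 for grading. Each possible class is therefore taken in turn, without assuming which ones occur.

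| Diagnosed SJS/TEN, by class (assumed) | Section 5.2.1 lists, read alone | Appendix D skin note |
|---|---|---|
| First severe or grade 3 reaction, not life-threatening | Withhold under the catch-all, then resume on recovery to grade 0-1 | Permanent stop, no exception in that line |
| Life-threatening or grade 4 | Permanent stop, waivable by the Sponsor/Medical Monitor | Same as above |
| Severe or grade 3 that recurs | Permanent stop, waivable | Same as above |
| Lower grade | No skin item in either list | Same as above |

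The table supports four statements.

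1. In the first row the results differ directly: resume against permanent stop.
2. In the second and third rows the default action agrees. The difference is the waiver, which 5.2.1 states and the note does not mention.
3. In the fourth row 5.2.1 gives no skin-specific action, while the note still does.
4. Other 5.2.1 provisions could also end treatment in a particular case: a treatment-related delay beyond 42 days, grade 2 or 3 reactions persisting at 12 weeks, or failure to taper corticosteroids within 12 weeks. Each has its own route to an exception by sponsor or Medical Monitor agreement, so none closes the gap.

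Next, does any text resolve the difference? Sections 5.1 and 5.2.1 call the Appendix D algorithms applicable, which favours reading the note as an addition to the lists. Section 5.1 also leaves modifications to the investigator's judgment, and Appendix D calls itself guidance. No precedence sentence appears in 5.1, 5.2.1 or Appendix D.

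Size: nivolumab is given in arms A and C, so 2 × 15 = 30 of the 45 planned patients are subject to these texts. The documents give no incidence for SJS or TEN, so the number affected cannot be derived from them. If it is assumed to be 0 or 1, the effect on the comparisons is negligible. The event itself is tabulated under Section 8.5.2 whichever text is followed. A patient whose SJS/TEN is graded 3 or 4 is already in that arm's grade 3-4 count, so a restart could not add that patient again. Nothing in the plan suggests that the week-6 PIS comparison would shift.

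**The case against.** The strongest reply is that the cross-reference already settles the matter. Section 5.2.1 brings in the skin algorithm, and a specific line about SJS/TEN would ordinarily qualify a general catch-all. On that reading the protocol is silent in one place and specific in another, which is not a contradiction. This is the sensible reading, and it stands as far as it goes. A reader might infer that the plan directs re-exposure, or that two binding rules give opposite orders. The documents support neither inference, because 5.2.1 declares the appendix applicable and the appendix calls itself guidance. What remains is that the protocol never states this reading as a rule, and that reading the texts together still leaves open whether the 5.2.1 waiver covers a diagnosed SJS/TEN.

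A second reply is that Appendix D does not exclude the Medical Monitor, since its opening lets discussion with that role supplement the guidance. That is correct. It would be too strong to say that Appendix D forbids a waiver. The accurate statement is that the SJS/TEN line contains none while the 5.2.1 list states one.

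A third reply is that the resume route needs a case that is neither grade 4 nor life-threatening, and the documents do not show that such a case exists. This also stands, and the grade is treated here as an assumption. The waiver difference does not depend on it.

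Finally, the investigator's judgment (Section 5.1), discontinuation for unacceptable adverse events (Section 6.7) and management according to product labels (Section 7.3) make an unconsidered restart less likely. So the right claim is that a site could restart, not that it would.

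**Conclusion.** The point holds as an internal inconsistency bearing on patient safety. For a diagnosed SJS or TEN, the 5.2.1 lists lead to resumption or to a waivable stop, the Appendix D note leads to a permanent stop with no stated exception, and the protocol does not say which governs. Re-exposure is a risk of applying the lists without the note, or of using the waiver; it is not what the plan as a whole clearly intends.

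A reader might also infer that the toxicity comparison would depend on which text a site followed. The documents do not support that: the event is counted either way, and they give no basis for expecting enough cases to matter.

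The conclusion rests on the readable note only, since the skin algorithm figure is not shown and its grade-by-grade boxes could not be compared with 5.2.1. The resume route also rests on the assumption that a diagnosed case can be below grade 4 and not life-threatening. No view is taken on which clinical rule is right.

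**What to change.** Amend the protocol in three respects.

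- Reconcile Section 5.2.1 with the Appendix D skin note for SJS/TEN, so that a site reaches the same action from either place.
- State whether the Sponsor/Medical Monitor approval in 5.2.1 reaches a diagnosed SJS or TEN.
- Add a sentence saying whether 5.2.1 or Appendix D governs when they differ.

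The sponsor and medical monitor decide the clinical content. As context, the document history for version 6.2 records the same kind of alignment with 5.2.1 for the gastrointestinal algorithm. The cost is a few lines in an amendment, with no added procedure, sample or visit and no change to the analysis.
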